The second metric reviewed was SAEs. The incidence of SAEs as reported for the adult VOR studies was 7%; 5% for the pediatric VOR studies, 0.8-10% for VPA studies, and 4.7-8.2% for AEDs. Given the differences in study designs and populations, the rates of SAEs are comparable. The most common SAEs reported in the adult VOR studies were thromboembolic events and anemia; in the pediatric VOR studies, SAEs consisted of thromboembolic events, bleeding/hemorrhage, neuropathy, and hypoxic/acute respiratory distress. Indeed the product monograph indicates that thromboembolic events maybe associated with VOR therapy with an overall incidence rate of 6.8%. However in the pediatric VOR studies, all SAEs were not considered to be related to VOR. Typically however, severity of events in cancer trials are graded using the National Institutes of Health CTCAE Grading system, whereas clinical trials typically utilize the International Council for Harmonisation of Technical Requirements for Pharmaceuticals for Human Use (ICH)/ Good Clinical Practice Guidelines (GCP) for rating severity of events. Utilizing the ICH-GCP definitions, a "serious" AE includes events that are life-threatening. Events rated as Grade 4 using the CTCAE system are considered to be life-threatening. Given this, Grade 4 events using the CTCAE reporting could be considered to be "SAEs". An analysis could not be carried out on the adult VOR studies because Grade 3 and 4 events were grouped together for reporting, however in the pediatric VOR studies, inclusion of the Grade 4 as SAEs caused the incidence rate of SAEs to jump to 65%, with again the most commonly reported events comprising hematologic events and nausea. Although this is an important consideration, it is also important to note that the term 'life-threatening' in the ICH/GCP definition of an SAE refers to an event in which the patient was at risk of death at the time of the event; it does not refer to an event which hypothetically might have caused death if it were more severe. It is not absolutely clear whether these Grade 4 events meet the ICH/GCP criteria for a serious event. However, the fact remains that Grade 4 hematologic events, which according to the CTCAE are platelets $< 25 \times 10^9/\text{L}$; absolute neutrophil count $< 0.5 \times 10^9/\text{L}$; and lymphocyte count $< 0.2 \times 10^9/\text{L}$; are medically quite serious, regardless of whether they meet a pre-set definition. As discussed in the above section, it is unlikely that the rates of incidence found in the Phase 1 VOR pediatric studies are expected in an overall medically stable population; it is anticipated that incidence of SAEs in the proposed population will be that typically seen with VPA/AEDs. However potentially serious hematologic events cannot be ruled out and hematologic testing, in addition to other lab safety testing will be conducted every 2 weeks to monitor study patients. Patients will also be advised of signs of symptoms associated with these hematologic events and to contact the study team in the event of these signs and symptoms. Regarding the other events cautioned to require special monitoring in

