3.1.2 PHASES OF STUDY

There are three phases to the study.

Phase 1: Screening period

During this phase, participants will be screened for study eligibility, which will last a total of 4 weeks. This will include several baseline investigations including full review of medical history and current medications, seizure frequency, physical examination, vital signs, laboratory safety testing, pregnancy testing for eligible patients, and electrocardiogram (ECG) (see Section 5 Schedule of Assessments and Procedures for complete list of screening procedures). In addition, baseline seizure frequency will be determined during this period. Clinically stable participants, fulfilling all eligibility criteria (see sections 4.2 and 4.3) will be enrolled in the treatment period of the study.

Phase 2: Treatment period

The duration of the treatment period will be 6 weeks. VOR will be given as fixed doses of 230 mg/m²/day. Following the enrollment visit, participants will visit the clinic for 2 more visits every 2 weeks, plus an end of treatment (EOT) visit (see Section 5.1 for detailed schedule). Participants may be seen more frequently for unscheduled visits for follow up of AEs, etc. as per the investigator's discretion. Study visits will include a physical examination, height and weight measurement, vital signs, pregnancy testing (required patients only). Safety monitoring during the treatment period will include laboratory safety testing and ECG. Investigators will review current medications, AEs, seizure diary/frequency at each visit. Investigators will assess study medication adherence at all visits; unused study medication will be returned to site at each visit and new study medication will be dispensed by local pharmacy, as recommended by the investigator. Unused study medication will be destroyed as per local standard operating procedures. All assessments and visit procedures will occur as stipulated in Section 5: Schedule of Assessments and Procedures.

Phase 3: Follow-up period

A safety follow-visit (SFU) will take place 6 weeks after the EOT Visit. The SFU visit will include a physical examination, height and weight measurement, vital signs. Safety monitoring for this visit will include laboratory safety testing and ECG. Investigators will review AEs since last visit and seizure diary/frequency. Any ongoing AEs will be followed by the investigator until resolution or stability.

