5.1 PROCEDURES

A detailed schedule of assessments by visit is shown in Table 5 below.

Table 5: Schedule of events

| Study Period | Screening | Enrollment | Treatment Period | | | Follow Up |
|-----------------------------------|-----------|------------|------------------|----------------|------------------|------------------|
| | | | Visit | V3 | V4 | |
| Visit | V1 | V2 | V3 | V4 | EOT ⁶ | SFU ⁷ |
| Total duration (weeks) | - 4 weeks | 0 | 2 | 4 | 6 | 12 |
| Visit windows (weeks) | | | ± 2 days | ± 2 days | ± 2 days | ± 5 days |
| Written informed consent | X | | | | | |
| Eligibility criteria | X | X | | | | |
| Medical history ¹ | X | X | | | | |
| Physical examination | X | | X | X ² | X | X |
| Complete Neurological examination | X | X | X | X | X | X |
| Anthropometrics | X | X | X | X | X | X |
| Vital signs ³ | X | X | X | X | X | X |
| Laboratory testing | X | | X | X | X | X |
| Serum Pregnancy test ⁴ | X | | | X | | X |
| Urine pregnancy test | | X | | | | |
| Study medication dispense | | X | X | X | | |

| | | | | | | |
|-------------------------------|----------------|---|---|---|---|---|
| Medication compliance audit | | | X | X | X | |
| Concomitant medication review | X | X | X | X | X | X |
| Seizure Frequency review | X | X | X | X | X | X |
| Adverse Events | | | X | X | X | X |
| ECG | X ⁵ | | X | | | X |

1. Medical history and Epilepsy history, including other relevant baseline disease characteristics. All available epilepsy history will be collected. Other Medical history will be collected for the past 12 months.
2. Abbreviated physical exam
3. Blood pressure, heart rate, breathing rate, and temperature.
4. Only for female patients of childbearing potential.
5. For screening, the results of a clinically indicated ECG, found to be non-clinically significant within the last 4 weeks can be utilized.
6. EOT may occur prior to 6 weeks if participant is discontinued or withdrawn before completing entire study as per protocol. In the case of withdrawal, the EOT visit should be completed within 2 weeks of the date of withdrawal.
7. SFU visit may occur prior to 12 weeks if participant is discontinued or withdrawn before completing entire study as per protocol. In the case of withdrawal, an SFU visit (or at minimum telephone contact) should be completed within 6 weeks of the EOT visit.

5.1.1 SCREENING EXAMINATION AND ELIGIBILITY SCREENING FORM – VISIT 1

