5.1.3 ASSESSMENTS AND PROCEDURES DURING THE TREATMENT PERIOD

Participants will be required to undergo regular visits during the treatment period for the assessments of safety/tolerability and efficacy as outlined in [Table 5: Schedule of events](#)

. They will visit the study center at 2-, and 4 weeks, at 6 weeks for the EOT visit, and 6-weeks after the EOT for the SFU visit. If a participant is discontinued from study medication and/or withdrawn prior to completing the study as per protocol, the EOT visit may occur prior to 6 weeks following enrollment. The SFU visit should be completed within 6 weeks of medication discontinuation.

In addition, the following evaluations will be performed at each visit at the clinic throughout the treatment period:

- Physical examination: standardized physical examinations will be performed at all study visits; an abbreviated physical exam will be conducted at Visit 4 (week 4 visit)
- Complete neurological examination: a complete neurological examination will be completed at all study visits.
- Anthropometrics: height and weight will be captured at all study visits to assess for appropriate growth and for proper medication dosing
- Vital signs: will be captured at all study visits
- Laboratory monitoring: participants will visit the lab for testing at all study visits during this period. Investigators will contact participants if results warrant intervention prior to the next scheduled visit.
- Pregnancy test: Serum pregnancy test will be taken at Visit 4.
- Study medication dispensing and medication compliance: Following investigator recommendation, participants will receive new drug supply at each defined visit. Participants will be required to bring in old unused drug for assessment of compliance. The importance of compliance will be emphasized at each visit. Participants will also be reminded to strive to consume enough fluids to maintain adequate daily hydration, as adjusted for age. Medication will not be dispensed at the EOT visit.
- Concomitant medications: will be reviewed at each study visit.
- Review of AE: Participant's AEs will be reviewed at each study visit. However participants are encouraged to inform investigators about occurrence of AEs as soon as possible; i.e. not wait until their next scheduled visit.

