5.3 SAFETY MONITORING

5.3.1 ADVERSE EVENTS

AEs (serious and non-serious) reported by the participant or observed by the investigator will be collected throughout the study. At each visit, the investigator will ask the participant if any untoward medical event occurred since the last visit. For each event, the date of onset and date of resolution, intensity, relationship to study medication, outcome and treatments administered for the event will be recorded in the study record.

AEs will include any symptom, sign, illness or experience, or clinically relevant lab abnormality, regardless of causality, which develops or worsens in severity during the course of the study. An SAE will comprise of any AE, occurring at any dose, regardless of causality that was either life-threatening, requires inpatient hospitalization or prolonging an existing hospitalization, or is determined as an important medical event by the treating physician, or results in death.

All AEs will be reported as stipulated in [Section 7.1](#). SAEs will be reported to the research ethics board (REB) and to Health Canada.

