8.2.2 ANALYSIS

8.2.2.1. SAFETY & TOLERABILITY ANALYSIS

Safety and tolerability will be assessed by calculating the incidence rate of AEs per number of drug days from the time medication is started through to the completion of the SFU (or 42 days following the last dose of study medication). This will be done for the following time points: 14 days following drug initiation; 30 days following drug initiation; 42 days following drug initiation; and 42 days following drug discontinuation. AEs will be further stratified by mild/moderate AEs, severe AEs, and SAEs, as well as project specific AEs (thromboembolism, hyperglycemia, gastrointestinal disturbances, dehydration, hematologic disturbances, QT/QTc prolongation).

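### Section 8.2.2.1 puts on-drug and post-discontinuation AEs on one drug-day rate, although the post-discontinuation period has no drug days and a third of the scheduled AE and laboratory checks

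*Combined protocol and SAP*

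**What the plan says.** Section 8.2.2.1 assesses safety by an AE incidence rate whose denominator is drug days, counted from first dose up to the safety follow-up visit (SFU) or 42 days after the last dose. It reports this rate at "14 days following drug initiation; 30 days following drug initiation; 42 days following drug initiation; and 42 days following drug discontinuation", with strata that include hematologic disturbances. It does not say whether each time point is cumulative or an interval, and it gives no denominator for days without drug.

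The visit schedule is in Table 5 (section 5.1), whose timing row reads "Total duration (weeks) | - 4 weeks | 0 | 2 | 4 | 6 | 12". Its rows for the two relevant checks are "Laboratory testing | X | | X | X | X | X" and "Adverse Events | | | X | X | X | X". Section 5.1.3 places the later visits "at 6 weeks for the EOT visit, and 6-weeks after the EOT for the SFU visit", and section 3.1.2 agrees: "A safety follow-visit (SFU) will take place 6 weeks after the EOT Visit".

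On ascertainment, section 5.3.1 says: "At each visit, the investigator will ask the participant if any untoward medical event occurred since the last visit". It also has onset and resolution dates recorded. Section 1.1.4.3 relies on frequent sampling to find blood-count problems: "hematologic testing, in addition to other lab safety testing will be conducted every 2 weeks to monitor study patients". That interval matches the treatment visits, not the follow-up period.

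Section 7.1.2 limits which laboratory abnormalities are recorded as clinically significant: those with symptoms, those that change study medication, and those that change concomitant therapy. Abnormalities meeting the SAE definition are reported as well.

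**The concern.** The rate in section 8.2.2.1 is the only analysis given for safety and tolerability, the trial's primary objective. The trial has one arm, and Table 5 schedules no AE review before the week 2 visit. The follow-up period is therefore the only other stretch of AE data against which a reader can set the on-drug rate. If the two periods are tabulated as one series of rates, the last figure should mean the same thing as the first three. As written it does not, for two reasons: its denominator is either carried over from the drug period or undefined, and scheduled checking falls from every 14 days to once in 42 days exactly when drug stops.

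The protocol expects hematologic events to be the distinctive risk. Those found only by blood sampling depend most on how often blood is drawn.

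**Working it through.** The plan states no AE rate, event count or power for this point, so there is no figure of its own to reproduce.

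**Step 1. Scheduled checks (Table 5).**
- On drug, 42 days: laboratory testing and AE review at weeks 2, 4 and 6, so 3 checks, one per 42/3 = 14 days.
- After stopping, 42 days: both at week 12 only, so 1 check per 42 days.
- ECG after first dose: one on drug (Visit 3) and one off drug (SFU), so 1 versus 1.

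**Step 2. What the rate means.** Take 12 children (section 3.3) who all complete 42 days, and an illustrative on-drug rate of 0.03 AEs per person-day (an assumption). On-drug AEs are 0.03 × 42 × 12 = 15.12 over 42 × 12 = 504 drug days. Let f be the captured off-drug rate as a fraction of the on-drug rate, so that off-drug AEs are 15.12f.

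| Reading of the last time point | Formula | f = 1 | f = 1/2 | f = 1/3 | f = 0 |
|---|---|---|---|---|---|
| Cumulative AEs per drug day (literal) | 15.12(1 + f)/504 | 0.060 | 0.045 | 0.040 | 0.030 |
| Off-drug AEs per off-drug drug day | 15.12f/0 | undefined | undefined | undefined | undefined |
| Off-drug AEs per off-drug calendar day | 15.12f/504 | 0.030 | 0.015 | 0.010 | 0 |
| Cumulative AEs per calendar day | 15.12(1 + f)/1008 | 0.030 | 0.0225 | 0.020 | 0.015 |

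The day-42 figure is 0.030 throughout. On the literal reading the last figure cannot fall below it, and it doubles to 0.060 when incidence is unchanged and fully captured. Early stopping enlarges the effect: a child who stops at day 14, with the same true incidence throughout, shows 0.03 × (14 + 42)/14 = 0.12 per drug day.

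**Step 3. Detection of a silent laboratory abnormality.** Assume it lasts D days, starts at a uniformly random time in the 42-day period, and is found only if a scheduled draw falls within it. The chance of detection is min(1, D/14) on drug and min(1, D/42) off drug. The documents give no durations, so D is shown as a range.

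| D (days) | On drug | Off drug | Off/on |
|---|---|---|---|
| 7 | 0.50 | 0.17 | 0.33 |
| 14 | 1.00 | 0.33 | 0.33 |
| 21 | 1.00 | 0.50 | 0.50 |
| 28 | 1.00 | 0.67 | 0.67 |
| 42 | 1.00 | 1.00 | 1.00 |

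**Step 4. Dilution by symptomatic AEs.** If a share s of AEs is symptomatic and captured equally in both periods, and the silent ones last 14 days, the overall ratio is s + (1 − s)/3. That is 0.33 at s = 0, 0.67 at s = 0.5, 0.83 at s = 0.75 and 0.93 at s = 0.9. The f = 1/3 column in Step 2 is thus an extreme in which every AE is a short silent laboratory finding.

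**Step 5. Which abnormalities count.** Under section 7.1.2 a symptom-free abnormality is recorded as clinically significant only if it changes study medication or concomitant therapy; otherwise it must meet the SAE definition. Once drug has stopped, the study-medication route is closed. This second asymmetry acts in the same direction as the sparser draws, and its size cannot be worked out from the documents.

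**The case against.** A reader might infer that the off-drug rate is bound to come out lower and will pass for recovery. The documents do not support that. On the literal drug-day wording the last figure cannot be lower than the day-42 figure for completers. A fall requires a calendar-day denominator that section 8.2.2.1 does not state. The plan also schedules no on/off comparison and draws no conclusion about reversibility: section 7.1.1.2 judges relatedness event by event, and section 8.2.1 sets the 12-child sample on feasibility, with no power calculation.

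The asymmetry is also narrower than the 3:1 count suggests. Clinical AEs are asked about over the whole interval and dated (section 5.3.1), and collection runs to 6 weeks after the last dose (section 7.2.1). Families are told to call about bruising or bleeding (section 7.1.3.1). Section 7.1.2 keeps most symptom-free abnormalities out of the AE count. ECGs are balanced. Children who stop early may have two off-drug contacts, because their end-of-treatment visit can fall up to 2 weeks after withdrawal.

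All of this stands, and it limits the point. It does not remove it. Repeat testing under section 7.1.3 follows abnormalities already found and does not detect new ones. The encouragement to report events early is in section 5.1.3, on the treatment period, and is not repeated in section 5.1.4. Uncertainty over the denominator does not protect the plan either: sparser capture lowers the last figure under every reading that can be computed, including the literal one (0.040 instead of 0.060 at f = 1/3).

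**Conclusion.** The point holds in a limited form. Section 8.2.2.1 uses one drug-day rate for periods that differ in both denominator and scheduled checking. Its last time point is an inflated cumulative figure, an undefined ratio or an unstated calendar-day rate, depending on the reading. Under a separate off-drug calendar-day rate, laboratory-detected AEs could appear at about one third of their on-drug frequency with no true change if they last 14 days or less, and at one half if they last 21 days. At 42 days or more there is no difference.

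These ratios rest on assumed durations, random onset and detection only at scheduled draws. They apply only to symptom-free laboratory abnormalities that qualify as AEs. Symptomatic AEs are exposed only to recall over 42 rather than 14 days, which cannot be quantified here, and QTc is not affected. The plan neither builds in a lower off-drug rate nor claims recovery. The defect is that its table would not let a reader tell.

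**What to change.** In section 8.2.2.1:

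1. Report the 42-day on-drug AE rate per drug day. Report the post-discontinuation AE rate separately, per off-drug person-day. State for every time point whether it is cumulative or an interval.
2. Report hematologic and other laboratory abnormalities as children abnormal over children sampled at each scheduled draw (weeks 2, 4, 6 and 12).
3. State that the on-drug and off-drug AE rates rest on different testing schedules (three draws versus one in 42 days) and should not be read as a direct comparison.

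This needs SAP wording and one extra table from data already planned, with no added visits or samples. The downside is that the simple side-by-side rate is given up.

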1.1.3 TOLERABILITY OF VORINOSTAT

In Phase 1 studies, VOR has been generally well-tolerated with drug limiting toxicities (DLTs)⁴⁴⁻⁴⁷.

- According to the VOR product monograph⁴⁰, AEs reported at greater than 10% incidence at a dose of 400 mg/day were: **fatigue** (45.3%), **diarrhea** (46.5%), **nausea** (38.4%), **thrombocytopenia** (25.5%), **dysgeusia** (23.3%), **anorexia** (23.3%), **weight decrease** (19.8%), **dry mouth** (16.3%), **alopecia** (16.3%), **muscle spasms** (16.3%), **anemia** (12.8%), **blood creatinine increase** (12.8%), **vomiting** (11.6%), **decreased appetite** (11.6%), **constipation** (10.5%), **chills** (10.5%).

- Of these AEs, the following occurred with a severity of Grade 3-4 (moderate – life threatening): **thrombocytopenia** (5.8%), **nausea** (3.5%), **muscle spasms** (2.3%), **anemia** (2.3%), **fatigue** (2.3%), **anorexia** (2.3%), **weight decrease** (1.2%), **decreased appetite** (1.2%), **chills** (1.2%), **dizziness** (1.2%), and **abdominal pain** (1.2%).
- SAEs outlined included events of **pulmonary embolism** (4.7%) and **anemia** (2.3%), as well as single experiences (1% incidence rate each) of thrombocytopenia, death of unknown cause, ischemic stroke, deep vein thrombosis (DVT), gastrointestinal hemorrhage, streptococcal bacteremia, dehydration and syncope, increased serum creatinine, decreased appetite, hypokalemia, leukopenia, nausea, neutropenia, and vomiting. There were a total of 5 deaths in these studies, which included disease progression, untreated sepsis, ischemic stroke and unknown cause; these were all considered unrelated to VOR.
- Regarding dose modification, 10.5% of patients required a dose modification due to AEs. AEs included: increased serum creatinine, decreased appetite, hypokalemia, leukopenia, nausea, neutropenia, thrombocytopenia, and vomiting. 10.5% of patients discontinued VOR due to AEs, these included: anemia, angioneurotic edema, asthenia, chest pain, death, DVT, ischemic stroke, lethargy, pulmonary embolism and skin lesions.

It is recommended by the product monograph that patients on VOR be closely monitored for several particular events, namely, thromboembolic events, QT/QTc prolongation, increased heart rate, hyperglycemia, dehydration, and hematologic events. In addition, VOR should be used with caution in special populations.

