- Thromboembolic events: a greater incidence of thromboembolic events appears to be associated with the use in VOR in adult patients with malignancies⁴⁸. In the pivotal study in patients with CTCL, the incidence rate of pulmonary embolism and DVT was 4.7%, and 1.2%, respectively⁴⁹. In all completed and ongoing studies in patients with CTCL, the proportion of patients with a venous thromboembolic event was 6.8%⁴⁸. In greater than a 1000 patients with hematologic malignancies and solid tumors who have been treated with VOR as monotherapy, or in combination with other chemotherapy agents, in completed and ongoing clinical studies, the proportion of patients that experienced a venous thromboembolic events was approximately 5.0%⁴⁸. In a double-blind study of patients with advanced non-small cell lung cancer who received VOR in combination with chemotherapy, there was an increase in the incidence of venous thromboembolic events as compared to patients who received chemotherapy alone; DVT and/or pulmonary embolism was reported in 6.5% (8/124) of patients in the VOR/chemo arm compared to 2.4% (3/124) in the placebo arm⁴⁸.
- QT/QTc prolongation: Use of VOR is reported to be associated with QT/QTc interval prolongation, which may lead to torsade de pointes; particular care should be exercised in patients with increased risk of experiencing torsade de pointes and patients on medications known to increase QT/QTc interval⁴⁸.
- Increased heart rate: Use of VOR is reported to be associated with increases in heart rate, which may lead to worsening of cardiac conditions in patients with history of cardiac problems⁴⁸.
- Hyperglycemia: Hyperglycemia is reported at an incidence rate of 4.7%⁴⁸ when using VOR.
- Dehydration: Reported as a common serious drug-related AE in clinical trials⁴⁸ with VOR.
- Hematologic events: Use of VOR is associated with dose-related thrombocytopenia and anemia⁴⁸.
- Special populations: VOR should with caution in patients with mild hepatic impairment; it is not recommended in patients with moderate hepatic impairment, and is contraindicated in patients with severe hepatic impairment.

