4.2 INCLUSION CRITERIA

Patients must meet **ALL** of the following criteria in order to be eligible for this study:

1. Males or females aged 2 – 17 years (inclusive)
2. Medically intractable epilepsy, defined as having failed at least 2 standard anti-seizures therapies and experiencing at least 3 motor seizures per week, separated by at least 24 hours that are quantifiable by observation (e.g. discrete episodes of motor activity). Participants experiencing other seizure types in addition to motor seizures may also be enrolled but must meet the minimal requirement for motor seizures.
3. Ability and willingness of family and/or caregiver (when appropriate) to give written informed consent and to comply with requirement of the study
4. Adequate bone marrow function (defined as an absolute neutrophil count (ANC) of $\geq 2 \times 10^9/L$; platelet count of $\geq 150 \times 10^9/L$; hemoglobin of ≥ 110 g/L [3-11 years], ≥ 120 g/L [females 12 years or over], ≥ 125 g/L [males 12-14 years], ≥ 137 g/L [males 15 years or older])
5. Adequate renal function (defined as serum creatinine $< 1.5X$ age-adjusted upper limit of normal [ULN], or glomerular filtration rate ≥ 70 mL/min/1.73 m²)
6. Adequate hepatic function (defined as total bilirubin < 1.5 times ULN, and alanine aminotransferase [ALT] and aspartate transaminase [AST] < 3 times ULN, and albumin > 33 g/L)
7. Corrected QT (QTc) interval of < 450 msec
8. Prothrombin time (PTT) < 1.5 ULN/International Normalized Ratio (INR) < 1.5 ULN
9. Participants on corticosteroids must be taking a stable or decreasing dose for at least 7 days prior to enrollment

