5.3.2.1 VITAL SIGNS

Seated blood pressure and pulse will be recorded after at least a 5-minute rest. Two measurements should be made for each blood pressure measurement and the average derived.

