7.1.3.1 Project Specific Adverse Events

The following AEs are noted in the VOR product monograph as warning and precautions, based on CTCL clinical trials in adults.

Thromboembolism

Pulmonary embolism and DVT have been reported as drug-related AEs in clinical trials with VOR. In greater than 1000 patients with hematologic malignancies and solid tumors who have been treated with VOR as monotherapy, or in combination with other chemotherapy agents, in completed and ongoing clinical studies, the proportion of patients that experienced a venous thromboembolic event was approximately 5.0%⁴⁰. An increase in the incidence of venous thromboembolic events was also found in patients with advanced non-small cell lung cancer who received VOR (400 mg once daily) in combination with chemotherapy (carboplatin and paclitaxel) as compared to patients who received chemotherapy alone. In this study, deep venous thrombosis and/or pulmonary embolism was reported in 6.5% (8/124) of patients in the VOR chemotherapy treatment arm compared to 2.4% (3/124) of patients in the placebo/chemotherapy treatment arm⁴⁰.

Investigators will closely monitor patients for signs and symptoms of these events, particularly in patients with a prior history of thromboembolic events. In the instance of a thromboembolic event, study drug will be discontinued.

Hyperglycemia

Hyperglycemia has been observed in patients receiving VOR⁴⁰. Serum glucose will be monitored as part of the biochemistry laboratory safety panel as summarized in [Table 5: Schedule of events](#).

. In the event of hyperglycemia, adjustment of diet or anti-hyperglycemic therapy may be trialed in the event of intolerable hyperglycemia.

Gastrointestinal Disturbances

Gastrointestinal disturbances, including nausea, vomiting and diarrhea have been reported very commonly in patients treated with VOR⁴⁰. Antiemetic and/or antidiarrheal medications may be trialed in the event of moderate to severe nausea, vomiting, diarrhea. Additional potassium and magnesium monitoring should be considered in symptomatic patients.

Dehydration

Dehydration has been reported as a common serious drug-related adverse experience in clinical trials⁴⁰. Participants will be instructed to consume enough fluids to maintain adequate daily hydration, as adjusted for age.

Hematologic Disturbances

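### Increased heart rate is named for close monitoring in 1.1.3 but is missing from the project-specific AEs, and no planned analysis uses the pulse measured at every visit

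*Combined protocol and SAP*

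**What the plan says.** Section 1.1.3 reports the monograph's advice that patients be "closely monitored for several particular events, namely, thromboembolic events, QT/QTc prolongation, increased heart rate, hyperglycemia, dehydration, and hematologic events". It then gives heart rate a bullet of its own: "Use of VOR is reported to be associated with increases in heart rate", with possible worsening of cardiac conditions in patients who have a cardiac history.

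Section 7.1.3.1 introduces the project-specific events with "The following AEs are noted in the VOR product monograph as warning and precautions, based on CTCL clinical trials in adults". The entries that follow are thromboembolism, hyperglycemia, gastrointestinal disturbances, dehydration, hematologic disturbances and QT/QTc prolongation. Heart rate has no entry.

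Section 8.2.2.1 assesses safety by "calculating the incidence rate of AEs per number of drug days". It splits AEs by severity and seriousness, and by "project specific AEs (thromboembolism, hyperglycemia, gastrointestinal disturbances, dehydration, hematologic disturbances, QT/QTc prolongation". No summary of vital signs or ECG intervals is planned there or elsewhere.

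Heart rate is a vital sign at every visit in Table 5 (Section 5.1), and 5.3.2.1 standardises it: "Seated blood pressure and pulse will be recorded after at least a 5-minute rest". ECGs are scheduled three times: screening, Visit 3 and the safety follow-up (SFU). QTc has a numerical limit in one place only, inclusion criterion 7 in Section 4.2: "Corrected QT (QTc) interval of < 450 msec". No correction formula is named anywhere.

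**The concern.** Safety and tolerability are the primary objective, and the protocol describes itself as the first trial of vorinostat in children with intractable epilepsy. An effect that the protocol attributes to the drug and singles out for monitoring should appear somewhere in the planned results. As written it does not. The measurements are made under standard conditions before, during and after treatment, and then feed no table. AE counts are a poor substitute, because no heart-rate threshold defines an AE. Whether a moderate symptom-free rise is recorded is left to judgement, and a modest shift shared by most participants may produce no AE at all.

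There is a secondary link to QT/QTc prolongation, which is on the list. QTc depends on how QT is corrected for rate, and the plan does not fix the correction. If the drug raises heart rate, part of any apparent QTc change could reflect the formula.

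**Working it through.** **1. The lists side by side**

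| Event | 1.1.3, close monitoring | 7.1.3.1 | 8.2.2.1 |
|---|---|---|---|
| Thromboembolism | yes | yes | yes |
| QT/QTc prolongation | yes | yes | yes |
| Increased heart rate | yes | **no** | **no** |
| Hyperglycemia | yes | yes | yes |
| Dehydration | yes | yes | yes |
| Hematologic events | yes | yes | yes |
| Gastrointestinal disturbances | no | yes | yes |

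Each list has six items and five are shared. Heart rate is the only event from 1.1.3 that does not carry over. The text gives no reason, although 7.1.3.1 says that it draws on the same monograph.

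**2. Where a heart-rate rise would appear if the plan is followed as written**

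- Recorded as an AE: it counts in the overall AE rate and its severity split, under no named category.
- Not recorded as an AE: it appears in no planned result, because the pulse values are not summarised.

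**3. What the existing schedule can support**

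Pulse is due at V1, V2, V3, V4, EOT and SFU. V2 is the last visit before dosing. V3, V4 and EOT cover the treatment period, and SFU follows 6 weeks later. Changes from V2 can therefore be computed with no new measurement. Only one ECG, at V3, is scheduled on treatment, so QTc can be compared at screening, V3 and SFU only.

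**4. Illustration of the QTc link (assumed values)**

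The plan has no figure to reproduce: the documents give neither the size of the heart-rate rise nor the correction in use. The inputs below are assumptions.

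With RR = 60/HR in seconds, Bazett is QTcB = QT/RR^(1/2) and Fridericia is QTcF = QT/RR^(1/3). Hence QTcB = QTcF × (HR/60)^(1/6). Hold QTcF at 400 msec, meaning no drug effect on repolarisation:

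- 80 beats/min: 400 × (80/60)^(1/6) = 419.6 msec
- 100 beats/min: 400 × (100/60)^(1/6) = 435.5 msec
- 120 beats/min: 400 × (120/60)^(1/6) = 449.0 msec

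A 20-beat rise adds 435.5 − 419.6 = 15.9 msec from 80, and 449.0 − 435.5 = 13.4 msec (unrounded inputs) from 100. Fridericia QTc does not move.

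Range: with QTcF between 390 and 420 msec and starting rates of 70 to 100 beats/min, the Bazett rise is about 3.5 to 5 msec for +5 beats, 7 to 10 msec for +10 and 13 to 18 msec for +20.

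The artefact can also run the other way. If QT truly followed the square-root relation with Bazett QTc constant at 420 msec, Fridericia QTc would fall by 14.6 msec for 80 to 100 beats/min and by 11.5 msec for 100 to 120. No single formula is safe by itself, so raw QT and heart rate should be shown beside QTc.

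**The case against.** **The AE route is open.** Sections 5.3.1 and 7.1.1 count any sign that develops or worsens as an AE. The clinical-significance filter in 7.1.2 applies only to laboratory results. Families are told to report palpitations, dizziness and syncope (5.1.2, 7.1.3.1). This stands. A reader might infer that the effect will be missed altogether or leave no trace, and the documents do not support that. What is lost is a named category and any view of the values themselves.

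**The pediatric evidence is reassuring.** Section 1.1.3 reports no cases of increased heart rate in the five pediatric oncology studies. However, the protocol does not offer this as its reason, and 1.1.4 says that those findings cannot be extrapolated to epilepsy. Section 1.1.3 also puts QT prolongation, hyperglycemia and dehydration below 1% each in those studies, yet all three stayed on the list.

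**The 450 msec limit.** A reader might infer that a drug-induced rise in heart rate could push a child past 450 msec and so be counted as QTc prolongation. It could not on this text. The limit is an entry criterion, judged on an ECG reviewed before enrolment, and no on-treatment QTc threshold is set.

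**The QTc figures are hypothetical.** This stands too. If the ECG laboratory already uses another correction, the artefact may be small or absent.

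**The sample is small.** There is one arm of 12 children. Section 5.2.1 expects up to 30% to discontinue for intolerable AEs (0.30 × 12 = 3.6 children), and 4.8 does not replace them and leaves some early non-safety withdrawals out of the final analysis. Complete pulse data from all 12 cannot be assumed, and a mean change cannot separate drug effect from visit-to-visit variation. This limits the table to description but is no reason to leave it out.

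**Conclusion.** The point holds as a minor one. Of the six events that 1.1.3 names for close monitoring, only increased heart rate is absent from both 7.1.3.1 and 8.2.2.1, and no planned analysis uses the pulse collected at every visit. This rests on the text alone and needs no assumption. The consequence is limited. A recorded rise still counts in the overall AE rate, but it cannot be seen as a category, and a moderate symptom-free shift across participants would not show.

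The QTc point is secondary and conditional. That no correction is named is a fact of the text. The 13 to 16 msec is an illustration that assumes Bazett correction, Fridericia QTc constant at 400 msec and a 20-beat rise from 80 or 100 beats/min. It shows why the formula should be fixed. It is not an estimate of what will happen in this trial.

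**What to change.** 1. Reconcile 1.1.3 with 7.1.3.1 and 8.2.2.1 by adding increased heart rate as a reported category in the latter two. This concerns reporting only and changes no dosing or stopping rule.
2. In 8.2.2.1, tabulate individual and mean change in seated pulse from V2 at V3, V4, EOT and SFU for participants with data, showing the number at each visit. Label the table descriptive.
3. Name one rate correction in advance, for example Fridericia. Report QT, heart rate and QTc from the same tracing at screening, V3 and SFU, with the ECG laboratory's own QTc value alongside. Do not cite 450 msec as an on-treatment limit.

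The cost is a short text amendment, one pulse table and one ECG table. No visit, test or participant burden is added. The only practical need is to keep the QT interval and heart rate from each ECG, including a screening ECG that was done earlier for clinical reasons, as 5.1.1 allows.
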